After 24 intervention sessions, patients are invited for the post-intervention assessment. This assessment will be scheduled as close as possible to the last training session. Participants will first evaluate the intervention with a non-blinded study member. Directly afterwards, participants will undergo a post-intervention assessment ('T1'). This assessment comprises a neuropsychological assessment and questionnaires (see Table 2). One team member (TB) will be de-blinded after the last T1 visit. All assessments after baseline will make use of parallel versions of neuropsychological tasks, if possible.

After six months ('T2'), one year ('T3') and two years ('T4'), participants will again undergo an extensive neuropsychological assessment and questionnaires. At T3 and T4, motor symptoms will also be assessed. From T3 onwards will be a naturalistic follow-up.

Blinding

Outcome assessors will be blinded for the full length of their role as assessor, while non-blinded team members will not assess participants at any point in this study. Blinded study members will not have access to the key of the randomization. Trial participants will be blinded for the full length of the study. Participants will be asked not to share any details of their intervention with the outcome assessor at any point in the study. When the participants' condition is revealed to an outcome assessor, he or she will be replaced by another assessor for this participant.

Drop-outs

Participants that drop out of the study after being allocated to an intervention condition will not be replaced. We expect a low drop-out rate on the basis of our pilot study (one drop-out in 21 participants) and the low burden and short duration of both training conditions. In our sample size calculation, we conservatively account for 10% drop-out.

In case a participant withdraws from the study after four weeks of training (or more), we will aim to schedule an exit-measurement to measure the intervention effect.

Medication adjustments

Participants and their neurologist will be requested to retain a stable medication regime during the study period, specifically during the intervention. Patients and their neurologist will be requested to inform the study team if medication changes are clinically necessary.

Table 2 Tabular overview of the study time schedule including assessments and visits.

Time-point	T-2	T-1	T0	T1	T2	T3	T4
Pre-screening							
Informed consent for pre-screening		X					
SAGE	X						

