The intervention in this study aims to train cognitive abilities, with a focus on executive functions, working memory, attention, and processing speed. A modified version of the BrainGymmer online CT platform (www.braingymmer.com), a product by Dezzel Media B.V.) is used to provide the training at the patients' home. We selected this method of cognitive training as it has been evaluated positively in our earlier pilot study in PD patients (see below), it is accessible for patients at home, and previous versions have been used in prior studies [59, 60]. A proof-of-concept in twenty PD patients showed that the experimental condition was evaluated as feasible and enjoyable. Moreover, the CT compared with an active control showed a medium interaction effect size on an executive functioning composite (i.e. Stroop Color Word Test, Trail Making Test and Controlled Oral Word Association Test), with a significantly positive change of executive functioning in the CT group but not in the active controls. Specifically, a large positive interaction effect size of CT on the Stroop color word test was found compared with controls (see Figure 2).

[figure not shown]

Figure 2 Change on median neuropsychological performance on left: an executive function composite score (consisting of standardized scores of the Stroop color word test card III corrected for card II, the Trail making test part B corrected for part A and the Controlled Oral Word Association Test) and right: the Stroop color word test card III corrected for card II. Significant differences are shown with the corresponding p value. Abbreviations: AC = active control condition; CT = cognitive training; EF = executive function; Stroop CWT = Stroop color word test.

Intervention characteristics

In both conditions, 24 training sessions are performed: three times a week for a length of eight weeks. The training sessions last approximately 45 minutes, marginally dependent on the participants' performance. Compliance and training performance data are automatically tracked when a participant performs a training session. Participants can independently schedule the three training sessions per week to ensure flexibility and a low training threshold. The training sessions can be paused at the participants' discretion but they are advised to try and complete the entire training within one hour.

Cognitive training

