- Data on physical activity at each visit will be measured by the New Zealand Physical Activity Questionnaire – Short Form, a structured interview on mild, moderate and vigorous physical activity, as physical activity is known to positively influence cognitive function and potentially provide a neuroprotective effect.[69, 70];
- We will rate motor symptom severity by the Unified Parkinson's Disease – Rating Scale part III and assess disease stage by the modified Hoehn & Yahr stage [71];
- Medication usage data are collected and transformed into a 'levodopa equivalent daily dosage' [33]. Dopamine replacement therapy may influence cognitive functions [72, 73];
- Intervention compliance will automatically be monitored by the training module. We will calculate total compliance as the proportion of completed training games out of 24 total sessions: $[N_{\text{completed}} / N_{\text{total}}] \times 100\%$, in which N_{total} is 13 games x 24 sessions in the CT

condition, and 3 games x 24 sessions in the AC condition. We define non-compliance as a completion rate lower than 75%, in accordance with Petrelli and colleagues [74].

ANALYSIS PLAN

Data-analyses will be performed on the Modified-Intention-To-Treat population, which comprises the compliant participants that underwent at least 75% of the intervention and at least one post-training assessment. We will compare the baseline characteristics of this sample to the Intention-to-Treat population (all randomized subjects). Secondary Per Protocol-analyses will be performed comprising the population that underwent the complete study protocol. Analyses will be performed with IBM SPSS version 22 (Armonk, NY, USA) and in R [75]. We will employ a statistical threshold of $\alpha = .05$.

The primary outcome will be analyzed using a multivariate mixed-model analysis using the accuracy on the five separate task-loadings (S1-S5) of the ToL at post-training visit (T1) as dependent measures, the training condition (CT vs. AC) as independent measure and baseline score of the outcome measures as covariates. We will construct a separate adjusted model with age, sex and years of education as additional covariates of no-interest. No imputation of missing values will be performed as this is not needed in linear mixed models.

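### Whether the T1 primary outcome is collected and used depends on adherence after randomisation, with gaps between the visit rules and the 75% analysis rule

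*Combined protocol and SAP*

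**What the plan says.** **Training schedule** (Intervention characteristics): "24 training sessions are performed: three times a week for a length of eight weeks". On pace: "Participants can independently schedule the three training sessions per week to ensure flexibility and a low training threshold".

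**T1 visit** (Post-intervention assessments): "After 24 intervention sessions, patients are invited for the post-intervention assessment". On timing: "This assessment will be scheduled as close as possible to the last training session". The text gives no latest date and no rule for someone who is still in the study but does not reach session 24. T2, T3 and T4 are set by elapsed time.

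**Withdrawal** (Drop-outs): "In case a participant withdraws from the study after four weeks of training (or more), we will aim to schedule an exit-measurement". The stated purpose is to capture the effect of the intervention. The documents do not say whether this visit includes the Tower of London or counts as T1. They are silent on withdrawal before four weeks.

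**Compliance** (Exploratory outcomes and covariates): "We define non-compliance as a completion rate lower than 75" per cent. The rate is counted in games, out of 13 x 24 in cognitive training (CT) and 3 x 24 in active control (AC).

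**Analysis** (Analysis Plan): the main population, labelled modified intention-to-treat, requires both 75% of the intervention and some post-training assessment. All randomised participants are used only for a comparison of baseline characteristics. The primary model takes Tower of London accuracy at T1 on five task loads, adjusts for baseline, and imputes nothing.

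**The concern.** Randomisation protects the CT versus AC comparison only if the outcome is sought and used in the same way whatever participants do afterwards. Here one set of rules decides who is measured and another decides who is analysed. Both depend on how much training was done, and they use different thresholds.

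The two conditions also differ in demand. CT is 13 games, most of them timed, whose difficulty adapts to keep participants at their limit. AC is solitaire, trivia and hangman. Stopping could therefore differ by arm, though nothing in the documents shows that it does. If it did, the participants who supply T1 data in the two arms would no longer be comparable, and the primary contrast would mix the training effect with selection. Where no measurement was taken, a later analysis of all randomised participants could not repair this.

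**Working it through.** **1. The thresholds on one scale.** Inputs are the sections cited above.
- Planned sessions: 3 per week x 8 weeks = 24.
- T1 invitation: 24/24 = 100% of sessions.
- Compliance: 0.75 x (13 x 24) = 234 of 312 games in CT; 0.75 x (3 x 24) = 54 of 72 in AC. With full sessions both equal 18 sessions (18 x 13 = 234; 18 x 3 = 54), or 18/3 = 6 weeks at the planned pace.
- Exit measurement: from 4 weeks x 3 = 12 sessions, or 12/24 = 50%.

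The session equivalents are approximate, because compliance counts games while the T1 rule counts sessions.

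**2. What the rules give each participant.**

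| Sessions done | Stays in the study | Withdraws |
|---|---|---|
| Under about 12 | No stated T1; outside main analysis | No stated measurement; outside main analysis |
| About 12-17 | No stated T1; outside main analysis | Exit measurement aimed for; outside main analysis |
| About 18-23 | **No stated T1, although compliant** | Exit measurement aimed for; compliant, but status as T1 not stated |
| 24 | Invited to T1; analysed if at least 75% of games done | Not separately addressed |

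**3. Whether the model makes up for a missing T1.** All five dependent measures in the primary model come from T1. A participant without T1 has none of them, and no other post-baseline visit is in the model. The statement that mixed models make imputation unnecessary therefore does not help such a participant. Someone with T2 but no T1 could meet the population definition and still add nothing to the primary result.

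**4. Power or selection?** The plan's 112 reproduces. With f = .12, r = .6, m = 2 measurements and alpha = .05, the noncentrality is f² x N x m/(1 − r) = 0.0144 x 112 x 2/0.4 = 8.06. Power is 0.804, and 112 is the smallest even N that reaches 80%. Taking that formula as given, with 140 randomised:
- T1 missing in 10% (126 left): power 0.848
- T1 missing in 20% (112 left): power 0.804
- T1 missing in 25% (105 left): power 0.778

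Moderate loss of T1 is affordable on the plan's own terms. The issue is selection.

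**5. Scale of selection, on assumed values only.** Let a share p of an arm lack T1, and let those missing score d SD below those observed, with the same d in both arms. The observed mean is then too high by p x d, and the contrast is biased by (p in CT − p in AC) x d. The documents give neither input. For an assumed arm difference of 5 to 10 percentage points and d of 0.3 to 0.8:
- lowest: 0.05 x 0.3 = 0.015 SD, which is 0.015/.23 = 7% of g = .23
- highest: 0.10 x 0.8 = 0.08 SD, which is 0.08/.23 = 35% of g = .23

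Equal loss in both arms gives zero on this formula. The range shows how the mechanism behaves and is not an estimate for this trial. It also ignores whatever the baseline covariate would absorb.

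**The case against.** The strongest reply is that nothing here is contradictory. One rule says when those who finish are invited, another says who is analysed, and the population definition separately asks for a post-training assessment. That is right. A reader might infer that the 24-session rule conflicts with the 75% rule, but the documents do not support this, because every rule can be followed at once. What remains is a set of gaps.

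A reader might also infer that everyone who stops at 18 to 23 sessions goes unmeasured. At the planned pace session 18 falls in week 6, so those who withdraw there are within the exit-measurement rule. Only those who do not withdraw are uncovered.

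A third tempting reading is a large delay in T1: at 2.25 sessions a week, 24/2.25 = 10.7 weeks, and at 2 a week, 24/2 = 12 weeks. This assumes training beyond the eight weeks the protocol describes. The stated flexibility concerns when the three weekly sessions take place, and no effect of delay on Tower of London accuracy is given. Testing close to the last session in both arms is also a defensible way to hold the retention interval constant.

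A fourth is a definite bias, such as 10% unmeasured x 0.5 SD = .05 SD, or 22% of g = .23. With equal loss in both arms the bias is 0.10 x (contrast in those observed − contrast in those unmeasured). An unmeasured contrast of −.5 SD gives .05 only if the observed contrast is zero. The 0.5 SD has no source in the documents.

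Three further points stand in part:
- Weekly compliance checks, biweekly questionnaires, phone follow-up and one drop-out among 21 pilot participants suggest small numbers. The pilot figure counts drop-outs, however, not incomplete training.
- The 24 sessions may be meant as the nominal end of eight weeks, and Figure 1, which is not shown, may give a T1 time. The text itself anchors T1 to the participant's last session.
- Withdrawers below 75% would be left out of the main analysis even if measured, so changing the visit rule alone would not bring them in. The analysis set has to change too.

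**Conclusion.** The point holds as a gap in the rules that is worth closing. As written, the primary outcome is collected and used conditional on adherence after randomisation. Three groups show this: compliant participants who do not withdraw but stop short of 24 sessions; withdrawers at about 12 to 17 sessions, whose exit measurement cannot serve its stated purpose in the main analysis; and earlier withdrawers, for whom no measurement is stated.

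The contrast is at risk if adherence differs by arm and is related to the outcome. Both conditions are plausible and neither is shown. The size is unknown, and the documents give no figure from which to estimate it. The conclusion rests on reading the T1 rule literally and on the text alone, without Figure 1.

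**What to change.** - **Visit rule.** Invite every randomised participant who has not refused further assessment to T1, including the Tower of London, at the end of the planned eight-week period, within a window stated in advance and whatever the number of sessions done. A rule of session 24 or a set week, whichever comes first, would still let pace determine timing for early finishers.
- **Exit measurement.** Drop the four-week condition, state the content of the visit, and count it as T1.
- **Analysis.** Analyse all randomised participants with a T1 value in the arm to which they were allocated. Keep the 75%-compliant analysis as secondary.
- **Reporting.** Give T1 timing, sessions completed and missing T1 by arm.

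If T1 collection is already complete, which the documents do not say, the reporting and the analysis of every available T1 and exit value in all randomised participants can still be done.

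The cost is protocol wording and a few extra visits of a type already planned. The estimate will be somewhat diluted because some T1 values will follow fewer sessions, and the secondary analysis remains for readers interested in compliant participants.

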imaging. See appendix 1 for the scan parameters. All assessments are performed by study members that are blinded for the treatment condition. The screening and baseline assessment will be performed during a single visit to the Amsterdam UMC, location VUmc.

Condition allocation and instructions

Following a positive screening for eligibility, a non-blinded study member will allocate the participant to either the CT or AC condition. Participants will be consecutively assigned to either the CT or AC condition on the basis of a randomization sequence. The randomization sequence is generated in Microsoft Excel by using computer-generated random numbers. We will use stratified randomization in which two strata will be generated according to education level. Vocational education level (or lower) defined as an education level of 5 or lower according to a Dutch classification system [56], which is comparable to 11 or less years of education [57]. High education level is defined as level 6 or 7 according to the Verhage classification system, which is comparable to 12 or more years of education.

A non-blinded study member will provide instructions to the participant concerning the log-in procedure for the training, the various training components, and the duration and frequency of training. After instructions, the participant will be asked to fill out a questionnaire concerning the patients' expectations and credibility regarding the intervention [58]. Participants will additionally receive a hand-out with instructions to take home.

Eight-week intervention period

After the baseline assessment, participants may directly start with the 8-week intervention. A detailed description of the CT and AC interventions is provided below. Compliance will be monitored automatically and will be checked weekly. During the intervention, patients will receive biweekly questionnaires to ensure compliance and check for questions and problems performing the intervention. Non-blinded study members will follow-up on potential problems by phone.

Post-intervention assessments

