An active control condition is used to correct for the nonspecific cognitive activity that participants in the CT group go through. In the control condition, participants undergo cognitive engagement using three games (i.e. solitaire, trivia questions and hangman) with a total duration of 45 minutes that will sequentially be performed and are hypothesized not to train specific cognitive functions.

Outcomes

Primary outcome

The primary outcome is the efficacy of CT on executive functions, measured by the percentage correct change score on a previously used computerized self-paced version of the Tower of London (ToL) task [29]. The ToL measures several aspects of executive functions, including planning, inhibition, and working memory [61]. This neuropsychological task consists of a model of three pins with different lengths, and three differently colored beads. In this task, the goal is to get from a starting position to a target position in as minimal steps as possible. There are five planning conditions that range in difficulty, with possible solutions ranging from one to five steps (i.e. task-load S1-S5). After nine exercise items with feedback, 100 pseudo-randomized test trials will be presented with a maximum response duration of 45 seconds per trial and no feedback on accuracy.

Secondary outcomes

The secondary outcome measures include (i) subjective cognitive complaints, (ii) cognitive function (other than the ToL) and (iii) structural and functional connectivity and brain network characteristics. All outcomes described below are changes after intervention relative to baseline.

- 1) Subjective cognitive dysfunction change after the intervention will be measured by the Parkinson's Disease Cognitive Functional Rating Scale (PD-CFRS, [62]) score and the Cognitive Failures Questionnaire (CFQ) score at the end of the intervention (T1), and at follow-up (T2, T3, and T4). We use the PD-CFRS questionnaire as a Parkinson-specific and sensitive measurement of subjective cognitive function. This questionnaire will be filled out by the participant and if possible by a caregiver. We will additionally use the CFQ as this measure has been used more frequently and it is more sensitive to small cognitive errors in daily living such as memory problems, absent-mindedness and slips of action[63];
- 2) Cognitive function change after the intervention will be measured by

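### The T1 visit puts an unregulated talk with an unblinded staff member directly before the outcome assessment, an avoidable route for expectancy cues, chiefly into the self-report questionnaires

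*Combined protocol and SAP*

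**What the plan says.** The section on post-intervention assessments fixes the sequence at the visit that closes the eight-week intervention. "Participants will first evaluate the intervention with a non-blinded study member". Then: "Directly afterwards, participants will undergo a post-intervention assessment ('T1"). On content it adds: "This assessment comprises a neuropsychological assessment and questionnaires (see Table 2").

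The primary outcome is obtained at this visit. The Outcomes section defines efficacy on executive functions as "measured by the percentage correct change score on a previously used computerized self-paced version of the Tower of London (ToL) task", and the Analysis plan uses "accuracy on the five separate task-loadings (S1-S5) of the ToL at post-training visit (T1) as dependent measures". The first secondary outcome, subjective cognitive dysfunction, is taken from the PD-CFRS and the "Cognitive Failures Questionnaire (CFQ) score at the end of the intervention (T1), and at follow-up (T2, T3, and T4").

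Under Blinding, the plan states: "Trial participants will be blinded for the full length of the study". The section on pre-screening, screening and baseline says: "All assessments are performed by study members that are blinded for the treatment condition". The Blinding section adds three working rules: unblinded staff never assess, participants are asked not to tell the assessor about their intervention, and an assessor who learns a participant's condition is replaced for that participant.

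**The concern.** The last event before the post-training measurements is a talk about the intervention with someone who knows which one the participant received. A remark, a tone or a leading question could tell a participant what to expect of the training just before the participant rates everyday cognitive failures, mood, anxiety or apathy. If such cues differed between the arms, they would enter the between-group contrast at T1. Adjusting for the baseline score would not remove them, because they would arise only at T1.

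They would also be hard to detect afterwards. The credibility and expectancy questionnaire is given once, after the training instructions, and Table 2 shows a single mark for it. Expectancy after training is not measured.

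**Working it through.** The plan gives no figure on this point and the documents supply none from which a bias could be computed, so no arithmetic applies. The sample size (112 required, 140 enrolled), alpha and power do not depend on the order of the visit. The check sets the relevant statements side by side.

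1. **Order.** The evaluation comes first and T1 follows directly. This is a stated procedure, not a missing detail. No reason is given for it, and nothing elsewhere in the document requires it.

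2. **Who conducts it.** A non-blinded study member, who knows the allocation.

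3. **What may be said.** No script, topic list, time limit or restriction is given. The document does not say whether perceived benefit is discussed or whether the talk differs between arms.

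4. **What the safeguards cover.** All three working rules under Blinding concern the assessor: who may assess, what the assessor may hear, and what happens if the assessor learns the condition. For the participant there is the statement that blinding lasts throughout, but no rule that governs this conversation.

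5. **Which outcomes are exposed.**
   - *Participant-completed scales* (PD-CFRS self-report, CFQ, and the other T1 questionnaires such as the Beck Depression Inventory, Apathy Scale and Parkinson Anxiety Scale): most exposed, since the participant's own judgement is the measurement.
   - *Caregiver PD-CFRS*: less directly exposed, since the caregiver is not described as taking part in the evaluation.
   - *ToL*: weakly exposed. It is computerized and self-paced, with 100 test trials and no feedback on accuracy. A cue could act only through effort. The order of tests within T1 is not given, so the evaluation precedes the T1 assessment as a whole but not necessarily the ToL immediately.
   - *T2 to T4*: no comparable evaluation is described before these visits, so the T1 contrasts are the ones concerned.

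6. **Condition for bias.** Both arms have the evaluation. A cue that acts equally in both cancels in the comparison; only a difference between arms biases it. Such a difference is possible, because the staff member knows the condition and the arms look different (13 games with adaptive difficulty against solitaire, trivia and hangman). It is not documented.

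7. **Avoidability.** The evaluation can follow the T1 assessment at the same visit with the same people.

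**The case against.** The strongest reply is that the plan says only that participants evaluate the intervention. Elsewhere it uses the same verb for the pilot finding that training was feasible and enjoyable, so a neutral usability debrief fits the text as well as a talk about benefit. This stands. A reader might infer that the conversation is about whether the training helped and that its content is arm-specific; the documents support neither statement.

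Second, the present order may have a purpose: participants talk about their training with the one person allowed to hear it before they meet the assessor. The plan does not give this reason, but it is plausible, and it makes the choice a trade-off. The balance still favours moving the evaluation. A slip to the assessor has little bearing on self-report scales or a computerized task, and rules on non-disclosure and replacement already exist for it. No written rule covers cues from the unblinded member to the participant.

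Third, unblinded staff already give the training instructions and telephone about problems during the eight weeks, so one more contact may add little. This is fair. Reordering removes only the contact closest to the measurements.

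**Conclusion.** The point holds as a minor design weakness. The protocol places an unregulated conversation with an unblinded person directly before T1, and this is avoidable. It matters mainly for the self-reported PD-CFRS and CFQ and the other T1 questionnaires, and only weakly, through effort, for the ToL. Bias would require the conversation to differ between arms, which is possible but not shown.

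Neither size nor direction can be derived. A reader might be tempted to express some small assumed shift as a share of the planning effect, g = .23. The documents do not support this: they give no value for the shift, and that effect concerns global cognitive function, not the questionnaires where the exposure lies.

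A reader might also infer that talking about the training first makes disclosure to the assessor more likely. The documents do not support that either. If anything, the risk of a slip may be slightly higher when the participant has not yet talked about the training, which is the downside of the change proposed here.

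The conclusion rests on reading the T1 questionnaires as part of the assessment that follows the evaluation, as the section says. Nothing indicates that they are completed beforehand.

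**What to change.** In the section on post-intervention assessments, state that participants complete all T1 questionnaires and tests first and then evaluate the intervention with the non-blinded study member, at the same visit. Repeat the existing instruction not to reveal the intervention to the assessor, in the invitation or on arrival.

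This needs no extra visit or scheduled staff and changes no sample size, alpha or power. The downside is that participants meet the assessor before they have talked about the training, so a slip may be slightly more likely on assessor-administered tests. The existing replacement rule then applies, and each use of it requires another blinded assessor.

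The documents do not say whether T1 visits are complete. If they are, the report should describe what the evaluation covered and state the order as a limitation, chiefly for the self-report outcomes.
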